4. GENERAL STATISTICAL CONSIDERATIONS

4.1. STATISTICAL HYPOTHESIS

There is no formal statistical hypothesis to be evaluated in this study; all statistical testing will be descriptive in nature.

4.2. SAMPLE SIZE

Approximately 100 patients in total are planned for enrollment in the study. Up to 69 patients will be enrolled to phase 1b with the actual number determined by the number of dose cohorts and number of patients in each cohort evaluated for determination of LANRA MTD/RP2D.

Approximately 31 patients are planned for enrollment in Phase 2. The optimal two-stage design to test the null hypothesis that the composite CR rate (CR/CRh) is $\leq 23\%$ (XOSPATA[®] [gilteritinib] US Prescribing Information, 2022) versus the alternative hypothesis, that CR/CRh is $\geq 23\%$ has an expected (average) sample size of 19.26 and a probability of early termination of 0.710. If the study regimen is not effective, there is a 0.025 probability of concluding that it is (the target for this value was 0.025 one-sided). If the study regimen is effective, as defined by CR/CRh = 46%, there is a 0.806 probability of concluding that it is (the target for this value was 0.800). (Calculations made using PASS 2020). After testing the treatment regimen on 12 patients in the first stage (including those treated at the MTD/RP2D in Phase 1b), the trial will be terminated if 3 or fewer patients respond. If the trial enrolls the second stage, additional patients will be enrolled to obtain at least 37 patients treated on the RP2D dose (including at least 6 patients enrolled to Phase 1b and treated at the RP2D). If the total number of patients enrolled to stage 1 and stage 2 who achieve a CR/CRh is ≤ 13 , the study regimen is rejected.

4.3. RANDOMIZATION AND MASKING

This is an open-label study. Patients who satisfy all inclusion and exclusion criteria will be enrolled into the next available patient slot.

4.4. HANDLING OF DATA

4.4.1. Strata and Covariates

There are no planned adjustments for covariates.

4.4.2. Examination of Patient Subsets

There are no planned subsets.

4.4.3. Multiple Testing and Comparisons

All analyses will be conducted without adjustments for multiple testing or comparisons.

4.4.4. Definitions and Data Derivations

Age

The age of a patient is defined as (Date of Day Informed Consent Signed – Date of Birth + 1)/365.25.

Cycle 1 Day 1

Cycle 1 Day 1 (C1D1) is defined as the earliest day that either study drug is administered.

Baseline Value

Baseline value is defined as the last observation of an assessment prior to the first dose of either study drug. For ECG assessments, the baseline value is the average of the predose triplicate measures taken on C1D1.

Study Day

Defined as the day relative to the administration of the first dose of either study drug (i.e., Cycle 1 Day 1). For events prior to C1D1, Study Day is calculated as:

$$\text{Study Day} = \text{event date} - \text{date of C1D1}$$

For events occurring on or after C1D1, Study Day is calculated as:

$$\text{Study Day} = \text{event date} - \text{date of C1D1} + 1$$

Post-Baseline Value

Any assessment occurring after the initiation of either study drug will be considered a post-baseline value. For assessments occurring on C1D1 where no time of assessment is captured, the value will be considered as post-baseline if the assessment was not planned as part of the set of predose/screening assessments (e.g., an assessment taken on C1D1 where no time was recorded but was not designated as a predose assessment will be considered a post-baseline assessment and an assessment on C1D1 without a time but designated as a predose assessment will be considered as such).

Change from Baseline

Change from baseline will be determined for post-baseline assessments (where applicable) as:

$$\text{Post-baseline value} - \text{baseline value}$$

Months since Initial Diagnosis

Months since initial diagnosis will be calculated as the actual number of calendar months between the date of initial diagnosis and C1D1.

Overall Duration of Exposure

The latest Date of either study drug – CID1 + 1. Dates of last dose are captured on the End of Treatment eCRFs.

Duration of Exposure to LANRA

Duration of exposure to LANRA will be defined as the Date of Last Dose of LANRA – Date of First Dose of LANRA + 1. The date of last dose is captured on the End of Treatment eCRF.

Duration of Exposure to Gilteritinib

Duration of exposure to Gilteritinib will be defined as the Date of Last Dose of Gilteritinib – Date of First Dose of Gilteritinib + 1. The date of last dose is captured on the End of Treatment eCRF.

Last Study Drug

The study drug with the latest date of exposure.

Cumulative Dose of LANRA

The sum of the LANRA doses administered to a patient measured in milligrams (mg)

Cumulative Dose of Gilteritinib

The sum of the gilteritinib doses administered to a patient measured in milligrams (mg)

Actual Dose Intensity of LANRA (mg/cycle)

Defined as the cumulative dose of LANRA / (duration of exposure / 28)

Actual Dose Intensity of Gilteritinib (mg/cycle)

Defined as the cumulative dose of gilteritinib / (duration of exposure / 28)

Relative LANRA Dose Intensity

Relative dose is set to $100 * (\text{Actual LANRA Dose Intensity} / \text{Expected Cumulative Dose} / 28)$

Relative Gilteritinib Dose Intensity

Relative dose is set to $100 * (\text{Actual Gilteritinib Dose Intensity} / \text{Expected Cumulative Dose} / 28)$

Treatment Interruptions

Treatment Interruptions will be defined as doses that are missed for any reason and will be calculated using the Dosing Log eCRF page by obtaining the number of missed doses over the duration of treatment.

Dose Reductions

Dose reductions will be defined as a planned reduction in dose level for AE management. These will be managed as noted in Table 2 (for gilteritinib) and Table 3 (for LANRA) of the protocol and identified by comparing the dose received as recorded in the Dosing Log eCRF page versus the dose assigned.

Duration of Follow-up

Duration of follow-up will be defined as the End of Study date – C1D1 + 1. End of study date is collected on the End of Study eCRF. Patients who are lost to follow-up will be censored at their date of last contact.

Measurable Residual Disease (MRD)

Presence of leukemia cells using a molecular characterization platform (eg. RT-PCR, NGS)

MRD Negative

A patient is considered MRD Negative if he/she has exhibits MRD negativity (<0.01%) in bone marrow as measured by a molecular assay for *FLT3* mutation (e.g., by next generation sequencing) in a central laboratory in the setting of a CR or CRh .

Overall Survival

The time from enrolment until death from any cause.

Complete Remission (CR)

Complete remission requires all of the following:

- Bone marrow blasts <5%
- Absence of circulating blasts and blasts with Auer rods
- Absence of extramedullary disease (ie. leukemia outside of bone marrow confirmed by biopsy)
- Absolute neutrophil count > 1.0 x 10⁹/L (1,000/μL)
- Platelet count > 100 x 10⁹/L (100,000/μL)

Complete Remission with partial hematologic recovery (CRh)

Complete remission with partial hematologic recovery requires all aforementioned CR criteria except for residual thrombocytopenia and/or neutropenia and is defined as:

- Bone marrow blasts <5%
- Absence of circulating blasts and blasts with Auer rods
- Absence of extramedullary disease
- Absolute neutrophil count > 0.5 x 10⁹/L (500/μL)
- Platelet count > 50 x 10⁹/L (50,000/μL)

Complete Remission with incomplete blood count recovery (CRi)*

Complete remission with incomplete blood count recovery requires all aforementioned CR criteria except for residual neutropenia or thrombocytopenia and is defined as

- Bone marrow blasts < 5%
- Absence of circulating blasts and blasts with Auer rods

- Absence of extramedullary disease
- Absolute neutrophil count $> 1.0 \times 10^9/L$ (1,000/ μ L) or platelet count $> 100 \times 10^9/L$ (100,000/ μ L)

*If patients meet criteria for both CRh and CRi, they should be classified as CRh

Morphological Leukemia Free State (MLFS)**

- Bone marrow blasts $< 5\%$
- Absence of blasts with Auer rods
- Absence of extramedullary disease
- No hematologic recovery required

** Marrow should not be merely “aplastic”, at least 200 cells should be enumerated or cellularity on bone marrow biopsy should be at least 10% of normal

Partial Remission (PR)

PR meets all hematologic criteria of CR:

- Absolute neutrophil count $\geq 1.0 \times 10^9/L$ (1,000/ μ L)
- Platelet count $\geq 100 \times 10^9/L$ (100,000/ μ L) *and*
- Residual bone marrow blast percentage of 5% to 25%
- Reduction of bone marrow blast percentage by $\geq 50\%$ compared with pre-treatment

Stable Disease

Absence of CR, CRh, CRi, PR, MLFS and criteria for PD not met.

Progressive Disease (PD)

Evidence for an increase in bone marrow blast percentage and/or circulating blast count as defined by at least one of the following:

- $>50\%$ increase in bone marrow blasts over baseline (a minimal absolute 15% increase is required in cases with $< 30\%$ blasts at baseline)
- Persistent bone marrow blast percentage $> 70\%$ over ≥ 3 months without at least a 100% improvement in absolute neutrophil counts (ANC) to an absolute level $> 0.5 \times 10^9/L$ (500/ μ L) and/or platelet count to $> 50 \times 10^9/L$ (50,000/ μ L) without transfusion
- $> 50\%$ increase in circulating blasts to $> 25 \times 10^9/L$ ($>25,000/\mu$ L) in the absence of Differentiation Syndrome***
- New Extramedullary disease

*** Certain targeted therapies, for example, those inhibiting mutant IDH proteins, other kinases or targets may cause a Differentiation Syndrome, i.e., a transient increase in the percentage of bone marrow blasts accompanied by an increase in circulating blasts. In the setting of therapy with such

compounds, an increase in blasts may not necessarily indicate progressive disease. Such instances should be discussed with the study medical monitor on a case-by-case basis.

Composite Complete Remission (cCR)

Achieving either complete remission or complete remission with partial hematologic recovery.

Duration of Response

Duration of response is defined as the time from first qualifying CR (CR or CRh) until relapse or death from any cause, as assessed by study investigators.

Event-free survival (EFS)

Event-free survival (EFS) is defined as the time from C1D1 until treatment failure (i.e., failure to achieve CR or CRh), relapse from CR/CRh or death from any cause.

Dose Limiting Toxicity

A DLT is defined as any of the following toxicities occurring within the DLT assessment period *unless it can be unequivocally determined to be unrelated to LANRA*:

- A nonhematologic toxicity of Grade ≥ 3 that is at least possibly related to LANRA with the exception of:
 - nausea, and vomiting controlled with antiemetic therapy,
(Note: Grade 3 nausea or vomiting that requires tube feeding, total parenteral nutrition and/or initial or prolonged hospitalization for management will constitute a DLT. Grade 4 nausea or vomiting will always constitute a DLT regardless of management.)
 - infection or infection-related toxicities such as fever/sepsis, febrile neutropenia*,
 - fatigue, alopecia,
 - isolated electrolyte abnormalities (ie. those without clinical consequences) correctable to Grade ≤ 1 within 72 hours with or without supplementation,
 - Grade 3 or 4 Differentiation Syndrome successfully managed with high-dose steroids plus supportive care interventions with resolution within 7 days and without resulting end-organ damage.
- Any toxicity resulting in administration of $< 80\%$ of the cumulative, Cycle 1 dose for either LANRA or gilteritinib.
 - Note: Administration of $< 80\%$ of the cumulative Cycle 1 dose for LANRA or gilteritinib for reasons other than toxicity (eg, non-compliance or administrative reasons) will not be considered a DLT but will make the subject unevaluable for purposes of MTD determination and require the subject to be replaced.
- Grade 4 neutropenia or thrombocytopenia lasting > 28 days after treatment onset that is not attributed to active AML and at least possibly related to LANRA.

- Any toxicity resulting in reduction in the dose of LANRA in Cycle 1.

*In general, infection will not constitute a DLT unless it is assessed as having resulted from unexpectedly prolonged myelosuppression in the setting of < 5% blasts in the bone marrow, absence of myelodysplastic changes, and/or absence of AML by flow cytometry in the bone marrow.

Adverse Event

An AE is defined as any unfavorable or unintended sign, symptom, laboratory abnormality or disease (new or exacerbated) temporally associated with the use of a study drug, whether considered causally related to the study drug or not.

All AEs defined as reportable in Section 16.6 of the protocol will be recorded on the ADVERSE EVENTS CRF.

Treatment-emergent Adverse Event (TEAE)

Any adverse event that occurs on or after C1D1 and up to the End-of-Treatment visit following discontinuation of the last study drug is considered treatment-emergent.

Events that occur after the initiation of non-protocol anti-leukemic therapy will be considered as non-treatment emergent even if they occur before the End-of-Treatment visit.

Treatment-emergent Laboratory Toxicity (TELT)

A TELT is identified based on the laboratory data recorded in the eCRF and is defined as a National Cancer Institute - Common Toxicity Criteria for Adverse Events (NCI-CTCAE) v5.0 (NCI 2017) grade 1 or higher abnormality, which occurs on or after C1D1 and up to the End-of-Treatment visit and exhibits at least 1 grade shift from the baseline value.

Events that occur after the initiation of non-protocol anti-leukemic therapy will be considered as non-treatment emergent even if they occur before the End-of-Treatment visit.

Concomitant Medications

Concomitant medications are those medications taken on or after C1D1. This includes medications started prior to C1D1 and continued after C1D1. These medications will be recorded in the PRIOR/CONCOMITANT MEDICATION eCRF.

Prior Medications

Prior medications are those medications taken from the time of informed consent until C1D1. These medications will be recorded in the PRIOR/CONCOMITANT MEDICATION eCRF.

End of Study

After all enrolled patients either relapse or die or 5 years after the last patient enrolls (whichever is earlier) or if the sponsor decides to terminate the trial.

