ⁿ LANRA will be dispensed by study center personnel at the beginning of each 28-day cycle to ensure adequate drug supply for home administration throughout the treatment phase in accordance with details outlined in the Pharmacy Manual. Instructions will be provided to patients for dosing, storage and disposition of unused study drug. In Phase 1b, patients will receive LANRA *only* on C1D1 under medical supervision after predose PK/PD blood samples are obtained.

Beginning on C1D2, patients will begin combination therapy with LANRA and gilteritinib, after the C1D2 (Hour 24) PK/PD blood samples are obtained (see [Table 4](#)). In Phase 2, patients will begin combination therapy with LANRA and gilteritinib on C1D1.

° Record all treatment-emergent adverse events including clinically relevant laboratory abnormalities on the adverse event eCRF. Treatment-emergent events are those that either begin or increase in intensity on C1D1 through the End-of-Treatment Evaluation. Record only serious adverse events that occur during the Screening evaluation. Events that meet the criteria for seriousness must be reported immediately, without undue delay, and within 24 hours to Kronos Bio Drug Safety (or designee). All adverse events are graded for severity using NCI-CTC AE, v. 5.0. See [Section 16.0 of the protocol for further details on AE reporting](#).

^p Record all medications (including over-the-counter medications) patient is taking from the time of informed consent until C1D1.

^q Record all new or continuing medications patient is taking from C1D1 until the End-of-Treatment Visit.

^r All male patients capable of fathering a child and WOCBP should be counseled regarding the need for pregnancy prevention in accordance with guidelines outlined in [Appendix 6](#) of the protocol.

^s The End-of-Treatment Study Visit must occur 30 ± 7 days after the last dose of either gilteritinib or LANRA (whichever is later) or prior to initiation of new anticancer therapy.

^t During the treatment phase, these assessments may be performed at a licensed facility other than the trial site up to 1 day prior to a scheduled study visit.

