5.1. DLT EVALUABLE POPULATION

Patients will be evaluable for DLT in Part 1 if they meet the following criteria:

- They experience a DLT (as defined in Appendix 1 of the study protocol) after receiving ≥ 1 dose of LANRA during the DLT assessment period (Cycle 1, Day 1 until Cycle 2, Day 1).
- They receive at least 80% of the intended cumulative doses of LANRA and gilteritinib during the DLT assessment period without the occurrence of a DLT.

The DLT Evaluable Population will be used for all DLT data summaries.

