5.2. SAFETY POPULATION

The Safety Population consists of all patients who receive ≥ 1 dose of either study drug and have at least 1 on-treatment safety-related observation, where a safety-related observation is defined as a reported AE or post-baseline assessment of vital signs, ECGs or safety laboratory assessments.

Patients will be analyzed according to their assigned dose level. The safety population will be used for all summaries of Safety data.

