6.4. EXPOSURE TO TREATMENT

Duration of exposure, cumulative dose, actual and relative dose intensities will be summarized for LANRA and gilteritinib. Treatment interruptions, dose reductions and reasons for discontinuation of gilteritinib/LANRA will be summarized by frequency distributions and percentages.

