10. PROPOSED TABLES, LISTINGS, AND FIGURES

Tables	
14.1.1	Subject Disposition and Discontinuation Summary, All Patients Enrolled: Phase 1b
14.1.2.1	Demographics, Safety Population : Phase 1b
14.1.2.2	Baseline Disease Characteristics, Safety Population : Phase 1b
14.1.4.1	Summary of Exposure, Safety Population: Phase 1b
14.1.4.2	Summary of Prior Antileukemic Regimens, Safety Population: Phase 1b
14.2.1	Summary of Best Response by ELN 2017 response criteria, Efficacy Evaluable Population: Phase 1b
14.2.2	Overall Survival, Safety Population: Phase 1b
14.3.1.1	Overview of Treatment Emergent Adverse Events, Safety Population: Phase 1b
14.3.1.2	Treatment-Emergent Adverse Events by System Organ Class, Preferred Term (All Cycles), Safety Population: Phase 1b
14.3.1.3	Treatment-Emergent Non-Serious Adverse Events by System Organ Class, Preferred Term (All Cycles), Safety Population: Phase 1b
14.3.1.4	Grade 3 or 4 Treatment-Emergent Adverse Events by System Organ Class, Preferred Term and Greatest Severity (All Cycles), Safety Population: Phase 1b
14.3.1.5	Treatment-Emergent Serious Adverse Events by System Organ Class, Preferred Term (All Cycles), Safety Population: Phase 1b
14.3.1.6	Treatment Related Adverse Events by System Organ Class, Preferred Term (All Cycles), Safety Population: Phase 1b

14.3.1.7	Treatment Emergent Adverse Events Leading to Dose Reduction by System Organ Class, Preferred Term (All Cycles), Safety Population: Phase 1b
14.3.1.8	Treatment Emergent Adverse Events Leading to Treatment Discontinuation by System Organ Class, Preferred Term (All Cycles), Safety Population: Phase 1b
14.3.1.9	Treatment Emergent Adverse Events Leading to Death by System Organ Class, Preferred Term (All Cycles), Safety Population: Phase 1b
14.3.2	Select Grade 3 or 4 Treatment-Emergent Laboratory Toxicities, All Cycles, Safety Population: Phase 1b
14.3.3	Electrocardiogram by Worst QTcF Results: Phase 1b
Listings	
16.2.1	Subject Disposition, All Patients Enrolled: Phase 1b
16.2.2.1	Informed Consent, All Patients Enrolled: Phase 1b
16.2.2.2	Subject Eligibility, All Patients Enrolled: Phase 1b
16.2.3	Analysis Populations, All Patients Enrolled: Phase 1b
16.2.4.1	Demographics, All Patients Enrolled: Phase 1b
16.2.4.2	General Medical History, All Patients Enrolled: Phase 1b
16.2.4.3	AML Diagnosis, All Patients Enrolled: Phase 1b
16.2.4.4	Additional AML Details, All Patients Enrolled: Phase 1b
16.2.4.5	Prior Systemic Anti-Leukemia Regimens, All Patients Enrolled: Phase 1b

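### SAP 4.4.4 divides relative dose intensity by an undefined cumulative dose and again by 28, so a fully adherent LANRA patient scores 3.57% at 28 days instead of 100%

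*SAP*

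**What the plan says.** SAP 4.4.4 builds the variable in two steps. Actual dose intensity for LANRA is "Defined as the cumulative dose of LANRA / (duration of exposure / 28"), labelled mg/cycle, and gilteritinib has the matching definition. Relative dose intensity is then 100 times the actual dose intensity divided by "Expected Cumulative Dose} / 28", with the same expression for both drugs. The brace inside the quote is left over from formula typesetting.

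The same section defines three durations: overall, LANRA and gilteritinib. The last begins "Duration of exposure to Gilteritinib will be defined as the Date of Last Dose of Gilteritinib" and subtracts the first gilteritinib dose date, plus one day. The dose-intensity formulas do not say which of the three they use. The choice matters in Phase 1b because LANRA is given alone on C1D1: "Beginning on C1D2, patients will begin combination therapy with LANRA and gilteritinib" (SAP 2.2, footnote n).

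SAP 6.4 plans the output: "actual and relative dose intensities will be summarized for LANRA and gilteritinib". It belongs to Table 14.1.4.1, "Summary of Exposure, Safety Population: Phase 1b". Protocol 15.2.8 announces the same summary and gives no formula.

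**The concern.** The numerator is already a rate per 28 days. On the natural reading the denominator is a total in mg, and the result is divided by 28 once more. The scales do not match, so the percentage cannot be read as the share of planned dose received.

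If the denominator is the expected total over the patient's exposure, the result is adherence divided by days on treatment. Patients who stay on treatment longer then score lower for the same adherence, and comparisons between dose groups are confounded with time on treatment. No single rescaling repairs that.

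The stakes are limited to a descriptive table. However, SAP section 7 restricts the analysis to Phase 1b, where safety is the primary objective, and the exposure table is part of how tolerability by dose level is described. SAP Appendix A relies on independent programming for verification. Two programmers facing an undefined term may diverge, or may both code the literal formula and agree on a wrong value.

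**Working it through.** **Inputs**

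- Actual dose intensity: A = C / (D/28), with C the cumulative dose in mg and D the duration of exposure in days (SAP 4.4.4).
- Relative dose intensity: R = 100 × (A / E / 28), with E the undefined term (SAP 4.4.4).
- Cycle length 28 days (SAP 2.2). LANRA 20, 40, 60 or 90 mg once daily; gilteritinib 120 mg once daily (SAP 2.1, Table 1).
- Gilteritinib from C1D2, so 27 doses in Cycle 1 (SAP 2.2, footnote n).
- E is an assumption, so several readings are tried.

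The documents state no numerical dose intensity, so there is no figure of the plan's own to reproduce.

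**General result for LANRA, full adherence.** At daily dose d over D days, C = dD and A = dD/(D/28) = 28d. The dose cancels in every case below.

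| Reading of E | Formula | 28 days | 84 days | 168 days |
|---|---|---|---|---|
| Total over exposure, dD | 100 × 28d/(dD)/28 = 100/D | 3.57% | 1.19% | 0.60% |
| Total per cycle, 28d | 100 × 28d/(28d)/28 = 100/28 | 3.57% | 3.57% | 3.57% |
| Total over exposure, bracketed as A/(E/28) | 100 × 28d × 28/(dD) = 78400/D | 2800% | 933% | 467% |
| Assigned daily dose, d | 100 × 28d/d/28 | 100% | 100% | 100% |

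The per-cycle total with the alternative bracketing gives 100 × 28d/(28d/28) = 2800% at any duration.

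**Worked case: LANRA 60 mg, 84 days, no missed dose**

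- C = 60 × 84 = 5040 mg; A = 5040/(84/28) = 1680 mg/cycle.
- As written, E = 5040: 100 × 1680/5040/28 = 1.19%.
- Per cycle, E = 1680: 100 × 1680/1680/28 = 3.57%.
- Denominator on the same scale, 60 × 28 = 1680: 100 × 1680/1680 = 100%.

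**Gilteritinib 120 mg, C1D2 to C1D28, no missed dose**

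- C = 120 × 27 = 3240 mg.
- Own duration, 27 days: A = 3240/(27/28) = 3360 mg/cycle. As written with E = 3240: 100 × 3360/3240/28 = 3.70%. At 83 and 167 days the same reading gives 100/83 = 1.20% and 100/167 = 0.60%.
- Corrected denominator, own duration: 100 × 3360/(120 × 28) = 100%.
- Corrected denominator, overall duration of 28 days: A = 3240 and 100 × 3240/3360 = 96.4%. The choice of duration therefore needs stating even once the denominator is right.

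**Misordering on the total-exposure reading, LANRA 60 mg**

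- 22 of 28 doses over 28 days: C = 1320 mg, A = 1320, E = 1680, R = 100 × 1320/1680/28 = 2.81%. True adherence is 22/28 = 78.6%.
- All 84 doses over 84 days: R = 1.19%. True adherence is 100%.

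The less adherent patient gets the higher score.

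**The case against.** The best defence is that only a word is wrong. With the assigned daily dose in place of E, the printed expression returns exactly 100% for full adherence, and the trailing division by 28 makes most sense on that reading. That may well have been the intention. But the SAP uses *cumulative* for totals: SAP 4.4.4 defines cumulative dose as a sum of doses administered, and the DLT rule in SAP 5.1 uses it for a total over a period ("They receive at least 80% of the intended cumulative doses of LANRA and gilteritinib during the DLT assessment period"). A programmer has no basis in the text for reading it as daily. If that was the intention, the term is mislabelled and still has to be changed.

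Second, the documents also speak of a cumulative dose for Cycle 1 alone (Protocol 13.0 and Appendix 1). On a per-cycle reading the error is a constant factor of 1/28 and patients keep their order. This stands: the misordering depends on the total-exposure reading. The constant value is still 3.57%.

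Third, the definitions are headed by drug, so the drug-specific duration is the natural one. That is fair. The effect for gilteritinib is 96.4% after Cycle 1 and 83/84 = 98.8% by day 84. It is a clarification to make alongside the main correction.

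Fourth, the consequence is small. Cumulative dose, duration and actual dose intensity are summarised too, and the dosing log is listed (Listing 16.2.5.2), so a reader could recompute the intended value. A score of 3.57% might also be noticed in verification. Both are true, and neither corrects the specification.

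**Conclusion.** The concern holds. No reading of the denominator as a cumulative dose returns 100% for a patient who takes every dose. On the total-exposure reading the LANRA value is 100/D, from 3.57% at 28 days to 0.60% at 168; on the per-cycle reading it is 3.57% throughout; with the alternative bracketing of the total it runs from 2800% down to 467%. The result does not depend on the LANRA dose level.

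Two assumptions carry this: that relative dose intensity is meant as the percentage of assigned dose received, and that *cumulative* has its ordinary meaning. The text is wrong as written, and the definition is also missing.

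The reach is narrow: one descriptive variable, for two drugs, in one table. Efficacy, the safety endpoints and DLT evaluability, which has its own 80% rule, do not use it. Cumulative dose and actual dose intensity do not use the faulty denominator. It should be corrected before the exposure table is produced.

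**What to change.** In SAP 4.4.4, replace the relative dose intensity definition for each drug with:

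100 × actual dose intensity (mg/cycle) / (originally assigned daily dose in mg × 28)

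Equivalently, 100 × cumulative dose / (originally assigned daily dose × duration of exposure in days). Full adherence then gives 100% at every dose and duration.

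Add a clause that actual and relative dose intensity both use that drug's own duration of exposure, as already defined in the same section.

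State that the denominator stays at the originally assigned dose after a reduction. This is an analysis convention to be declared. SAP 5.2 does not settle it, since it only fixes how patients are grouped ("Patients will be analyzed according to their assigned dose level"), but the convention fits that grouping, and it fits the SAP's own definition of a dose reduction, which compares the dose received with the dose assigned.

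The cost is one line per drug, the clauses above and a change to the derivation code. No new data are needed.
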